10.3 Statistical Analyses

The statistical analysis plan will be developed and finalized before database lock and will describe the selection of participants to be included in the analyses, and procedures for accounting for missing, unused, and spurious data. Below is a summary of planned statistical analyses of the primary and secondary endpoints.

10.3.1 Efficacy Analyses

Not applicable.

10.3.2 Safety Analyses

All safety analyses will be performed on the Treated Population.

Endpoint	Statistical Analysis Methods
Secondary: AEs, clinical laboratory	Descriptive summaries will be presented for continuous variables using number of participants (N), mean, standard deviation, median, minimum, and maximum. Descriptive summaries for categorical variables will utilize counts

values, vital signs, ECGs, or other safety biomarkers	and percentages. All recorded AEs will be listed and tabulated by system organ class, preferred term, treatment arm, and treatment. Vital signs, ECGs, and clinical laboratory test results will be listed and summarized by planned time point, treatment arm, and treatment. Marked abnormal clinical laboratory test results will be summarized by treatment arm and treatment. Any significant physical examination findings will be listed. Electrocardiogram readings will be summarized by planned time point, treatment arm, and treatment, and investigator-identified abnormalities, if present, will be listed.
---	--

10.3.3 Other Analyses

Endpoint	Statistical Analysis Methods
Primary: Change from baseline in thrombus area (post-treatment with BMS-986141 vs. pretreatment)	An analysis of variance will be performed on the natural logarithm (ln)-transformed thrombus area using general linear mixed effects models separately by shear rates (Low or High) with perfusion run (baseline, 2 hours, and 24 hours) as fixed effects and participant as a random effect. A supplemental analysis of variance will be performed on the natural ln-transformed thrombus area using general linear mixed effects models separately by shear rates (Low or High) with treatment arm, perfusion run (baseline, 2 hours, and 24 hours) as fixed effects and participant as a random effect. Means, mean differences from baseline, and the 95% CI of mean differences on the log scale will be estimated from the models and be exponentiated to express the results as geometric means, geometric mean ratios to baseline, and the 95% CI of geometric mean ratios on the original scale. All thrombosis chamber endpoints will be listed, plotted and summarized by treatment arm, shear rate, and perfusion run.

Summary statistics for each of the biomarkers and their corresponding percent changes from baseline will be tabulated by treatment arm, shear rate, and perfusion run. Plots of mean values of biomarkers, as well as geometric mean percent changes from baseline versus shear rate and perfusion run will be provided for each treatment arm. Potential correlation between BMS-986141 exposure and thrombus formation in an ex vivo porcine aortic thrombosis chamber and other biomarkers/PD markers will be explored.

Summary statistics for PK concentrations of BMS-986141, metabolite BMT-162856, ASA, salicylic acid, and ticagrelor will be tabulated.

10.3.4 *Interim Analyses*

Not applicable.

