4 OBJECTIVES AND ENDPOINTS

Table 4-1: Objectives and Endpoints

Objectives	Endpoints
Primary 
To assess the effect of BMS-986141 alone and as add on to ticagrelor, aspirin, or the ticagrelor + aspirin combination, on thrombus formation in an ex vivo porcine aortic thrombosis chamber model as compared to pretreatment	
Change from baseline in thrombus area (post-treatment with BMS-986141 versus pretreatment)
Secondary 
To assess the safety and tolerability of single doses of BMS-986141 when dosed with ticagrelor, aspirin, or the ticagrelor + aspirin combinationTo assess the safety and tolerability of ticagrelor, aspirin, or the ticagrelor + aspirin combination in participants with coronary artery diseaseTo assess the safety and tolerability of a single dose of BMS-986141 in normal healthy participants	
AEs, clinical laboratory values, vital signs, ECGs, or other safety biomarkersAEs, clinical laboratory values, vital signs, ECGs, or other safety biomarkersAEs, clinical laboratory values, vital signs, ECGs, or other safety biomarkers
[REDACTED]	[REDACTED]

Table 4-1: Objectives and Endpoints

Objectives	Endpoints
[REDACTED]	[REDACTED]

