- Treatment Arm 3: Single oral dose of 90 mg ticagrelor + 75 mg aspirin, followed by a single oral dose of 4 mg BMS-986141 approximately 2 hours later (Day 1). A second dose of ticagrelor will be taken approximately 12 hours after the first dose. Ticagrelor + aspirin dosing will continue on Day 2.

Approximately 10 normal healthy participants will be enrolled in Treatment Arm 4 and receive a single dose of 4 mg BMS-986141 on Day 1.

Participants will report to the clinical facility in the morning on Day 1 (Visit 1) prior to BMS-986141 dosing and will return to the clinical facility on Day 2 (Visit 2) approximately 1 hour prior to the final chamber run. Thrombus formation will be determined using the Badimon thrombosis chamber, according to the standard site procedures. Briefly, each participant will have blood drawn from a vein through a cannula set attached to extension tubing. The tubing will be connected to a series of 3 perfusion chambers containing denuded porcine aorta as a thrombogenic surface. A pump placed distal to the chambers will maintain a unidirectional flow at a rate of 10 mL/min. The rheologic conditions in the first chamber will be at a low shear rate (approximately 212 s^{-1}) simulating patent arterial flow. The shear rate on the second and third chambers will be high (approximately 1690 s^{-1}), simulating stenosed arteries. Each perfusion study will last for 5 minutes. The size of the thrombus formed on the denuded porcine aorta will be assessed by morphometrical analysis. A total of 3 perfusion runs will be performed per participant in each treatment arm.

[figure not shown]
For Treatment Arms 1, 2, and 3, a baseline chamber run will be performed on Day 1 approximately 2 hours after background therapy (ticagrelor, aspirin, or ticagrelor + aspirin) and prior to BMS-986141 administration. A second chamber run will be performed 2 hours following oral administration of BMS-986141. This second chamber run is designed to be conducted at the predicted Tmax of BMS-986141. Participants will be released from the clinic after the Hour 2 chamber run is complete and the Hour 2 PK sample is collected. Participants will return to the clinic on Day 2 approximately 1 hour before the final chamber run. Participants will receive background therapy before the final chamber run, and the final chamber run will be performed on Day 2, approximately 24 hours after BMS-986141 dosing. Participants will be discharged from

[figure not shown]

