9.8 Biomarkers

Thrombus formation will be determined using the Badimon chamber. Venous blood will be collected from study participants through a cannula set attached to extension tubing. The tubing will be connected to a series of 3 perfusion chambers containing porcine aorta as a thrombogenic surface. A pump placed distal to the chambers will maintain unidirectional flow at a rate of 10 mL/min. The rheologic conditions in the first chamber stimulate those of patent arteries (low shear rate, approximately 212 s^{-1}), and those in the second and third chambers simulate those of stenosed arteries (high shear rate, approximately 1690 s^{-1}). Each perfusion study will last for 5 minutes. Immediately after each perfusion, porcine strips with thrombus attached will be

removed and fixed, and total thrombus area will be assessed by morphometrical analysis.

Aortic strip analysis will be performed blinded. Aortic strips will be assigned and stored with a unique sample number unrelated to the participant number. Aortic stripes are then processed by the histology department, who are blinded to the study entirely, and analyzed at a later date by an operator blinded to the aortic strip linked sample numbers. Sample linkage will be kept securely in the study site.

Circulating biomarker assessment for this chamber study focuses primarily on PD biomarkers.

In addition, serum samples will be collected for assessment of SARS-CoV-2 serology.

Blood will be drawn at the times indicated in Table 9.8-1 and [Table 9.8-2](#). Further details of blood collection and processing will be provided to the site in the procedure manual.

Table 9.8-1: Biomarker Sampling Schedule - Treatment Arms 1, 2, and 3

Study Day of Sample Collection	Event	Time (Relative To BMS-986141 Dose) Hour:Min				Serum for SARS-CoV-2 serology
1	predose	-02:00				X
1		02:00				
2		24:00				

Abbreviations:

Table 9.8-2: Biomarker Sampling Schedule - Treatment Arm 4

Study Day of Sample Collection	Event	Time (Relative To BMS-986141 Dose) Hour:Min	■■■■■	■■■■■	■■■■■	Serum for SARS-CoV-2 serology
1	predose	00:00	■	■	■	X
1		02:00	■	■	■	
2		24:00	■	■	■	

Abbreviations: ■■■■■ = [REDACTED]

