10 STATISTICAL CONSIDERATIONS

10.1 Sample Size Determination

The sample size for this study is not based on statistical power, but based on consideration of the precision of the estimate of the effect of BMS-986141 alone and as add on to aspirin, ticagrelor, or the aspirin/ticagrelor combination, on thrombus formation in an ex vivo porcine aortic thrombosis chamber model as compared to pretreatment.

The half-width of the 95% CI of the change from baseline in thrombus area on the log scale after administration of BMS-986141 will be 0.146 or 0.188 if there are 15 or 10 participants per arm, respectively. This calculation assumes that the thrombus area is log-normally distributed and the change from baseline on the log scale has a standard deviation of 0.263 as observed in CV004-007.

The following table provides examples of 95% CIs of the true percent reduction in thrombus area after administration of BMS-986141, assuming the true percent reduction (percent decrease from baseline) is 15%, 20%, or 30%, and the sample size is 15 per arm or 10 per arm.

Sample Size per Arm	True Reduction from Baseline	Change from Baseline on Log Scale (95% CI)	Geometric Mean Ratio to Baseline (95% CI)
15	15%	-0.163 (-0.309, -0.017)	0.85 (0.73, 0.98)
15	20%	-0.223 (-0.369, -0.077)	0.80 (0.69, 0.93)
15	30%	-0.357 (-0.503, -0.211)	0.70 (0.60, 0.81)
10	30%	-0.357 (-0.545, -0.169)	0.70 (0.58, 0.84)

Approximately 55 participants (15 participants in Treatment Arms 1, 2, and 3, and 10 participants in Treatment Arm 4) are planned to be dosed with BMS-986141.

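### Does leaving the two high-shear strips per run uncombined in section 10.3.3 put the high-shear confidence intervals at risk?

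*Combined protocol and SAP*

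**What the plan says.** Section 5.1 describes blood drawn through tubing "connected to a series of 3 perfusion chambers containing denuded porcine aorta". The first chamber runs at low shear. For the others, "The shear rate on the second and third chambers will be high", and section 9.8 agrees that "those in the second and third chambers simulate those of stenosed arteries". With three runs per participant, that is three low-shear and six high-shear strips each. Section 9.8 then has total thrombus area measured by morphometry, without saying whether the total is per strip or across the two high-shear strips.

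Section 10.3.3 fits log thrombus area in separate low- and high-shear mixed models "with perfusion run (baseline, 2 hours, and 24 hours) as fixed effects and participant as a random effect". A supplemental model adds treatment arm. Neither has a participant-by-run term or a chamber term. The same section adds: "All thrombosis chamber endpoints will be listed, plotted and summarized by treatment arm, shear rate, and perfusion run".

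Section 10.1 sizes the study on precision. The half-width of the 95% interval "will be 0.146 or 0.188 if there are 15 or 10 participants per arm, respectively", on the assumption that "the change from baseline on the log scale has a standard deviation of 0.263 as observed in CV004-007". Section 10.3 describes what follows it as a summary and leaves further detail to a statistical analysis plan, to be finalised before database lock.

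**The concern.** Two strips perfused in series with the same blood, through the same cannula and in the same five minutes, are unlikely to be independent once the participant effect is removed. A model whose only random effect is participant treats them as if they were. Applied to strip rows, it pools two kinds of variation: how a participant's runs differ from one another, which is the correct yardstick for a change from baseline, and how the two strips within a run differ, which is not. It also has no place for a systematic difference between chambers 2 and 3.

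The error could go either way. Correlated strips make the interval too narrow; a large chamber difference makes it too wide. Because section 10.1 justifies the sample size by interval width and not by power, a misstated width would affect the quantity the study was sized to deliver. Low shear, with one strip per run, is not exposed.

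**Working it through.** **Which unit the plan uses.** Inputs from section 10.1: SD of change 0.263; n = 15 or 10. Half-width = t(0.975, n−1) × 0.263/√n.

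- n = 15: 2.145 × 0.263/3.873 = 0.1456, stated as 0.146.
- n = 10: 2.262 × 0.263/3.162 = 0.1881, stated as 0.188.

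A normal quantile gives 0.133 and 0.163, which do not match. The sizing therefore takes one change per participant, with n participants in an arm.

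**What a strip-level fit would do.** Assumptions not in the documents: strips enter as rows; 0.263 is the SD of the change in the two-strip mean; the model is fitted within an arm; ρ is the same-run correlation after removing participant; d is the chamber 2 versus 3 shift in log area. Let su² be the run-within-participant variance and se² the strip variance. Then 2su² + se² = 0.263² = 0.0692 and ρ = su²/(su² + se²).

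The participant-only model has expected mean square

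[2(n−1)(se² + 2su²) + 3n(se² + d²/2)]/(5n−2),

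where the correct value is se² + 2su² = 0.0692. In both cases the variance of a run difference is the mean square divided by n.

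Example, n = 15, ρ = 0.5, d = 0: su² = se² = 0.0692/3 = 0.0231. The mean square is (28 × 0.0692 + 45 × 0.0231)/73 = 0.0408. The half-width is t(73) × √(0.0408/15) = 1.993 × 0.0521 = 0.104. With one value per run it is t(28) × √(0.0692/15) = 2.048 × 0.0679 = 0.139.

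Simulation, 20,000 trials per setting (average half-width, coverage):

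| ρ | d | Strip rows, n = 15 | Strip rows, n = 10 |
|---|---|---|---|
| 0 | 0 | 0.135, 95.1% | 0.166, 95.1% |
| 0.25 | 0 | 0.117, 91.2% | 0.144, 90.9% |
| 0.5 | 0 | 0.103, 87.1% | 0.127, 86.3% |
| 0.75 | 0 | 0.092, 82.3% | 0.113, 81.6% |
| 0 | 0.30 | 0.160, 97.8% | 0.197, 97.8% |
| 0.5 | 0.30 | 0.134, 95.1% | 0.166, 95.3% |
| 0.25 | 0.40 | 0.164, 98.3% | 0.202, 98.4% |

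One value per run averages 0.138 (n = 15) and about 0.172 (n = 10), with coverage of about 95% in every row.

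**Effect on the section 10.1 examples.** The 15% reduction at n = 15 is the most fragile row: its interval excludes a ratio of 1 only while the half-width stays below |ln 0.85| = 0.1625. At ρ = 0.1, d = 0.30 the half-width is 0.153 and the upper limit is about 0.99. At ρ = 0.25, d = 0.40 it is 0.164, and the interval just reaches 1. So a strip-level fit could, with a large enough chamber difference, alter the reading of that row.

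**The case for a change.** The strongest case for a change is that section 10.3.3 already fixes the transformation, the fixed effects and the random effect, so it should also name the row to which they apply. The list of matters that section 10.3 leaves to the later plan covers participant selection and missing, unused and spurious data, not the unit of analysis. Positive same-run correlation is plausible, and coverage near 82% would be a real fault. The mean of the log areas and the log of the summed areas are also different quantities, so an open rule leaves some choice after the data exist.

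The textual point stands: no section states the rule, and the total area in section 9.8 does not supply it. The arithmetic stands too, under its assumptions. But the harm requires an analyst to choose strips as rows, which no section calls for and which would depart from the unit in section 10.1. A list of a few topics for the later plan is not a bar on covering others. The choice between mean and sum is real but limited: the strips are read blinded, the analysis plan must be final before database lock, and either reduction keeps coverage close to 95%.

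**Conclusion.** No change to the plan is needed. This is a gap that analysts fill sensibly. The sizing calculation, the endpoint defined in section 4 as a change from baseline, and the summaries by arm, shear rate and run all point to one high-shear value per participant per run. On that reading the participant-only model gives sound intervals at both shear rates.

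The size of the alternative depends on inputs the documents do not give. Over the settings tabulated, coverage for a strip-level fit runs from about 82% to 98%. It is about 95% when strips are uncorrelated and the chambers agree, or when the two effects cancel. Neither the direction nor the amount of any error can be read from the protocol. Whether the primary model is fitted within each arm is likewise unwritten; section 10.1 implies that it is, and the coverage pattern does not depend on it: a single fit to all 55 participants with no chamber difference gives 91% and 87% at ρ = 0.25 and 0.5.

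The conclusion rests on the analysis using one value per run. The later analysis plan is the natural place to record how chambers 2 and 3 are combined.

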5.5 Justification for Dose

Single doses of BMS-986141 have been evaluated up to 150 mg and multiple doses up to 30 mg once daily for up to 14 days in study CV006003 with acceptable safety and tolerability. BMS-986141 has also been dosed 20 mg once daily for 14 days in the presence of 325 mg aspirin. No appreciable changes in PK, PD, or bleeding time were observed in the presence of aspirin. The PK were found to be dose proportional in the explored range. BMS-986141 is characterized by rapid absorption with maximal concentrations at 1 to 4 hours postdose and a terminal half-life of about 40 hours. Evaluation of exposures after daily dosing indicates an accumulation index of up to 1.9 and an effective half-life of about 22 hours, suggestive that once daily dosing would be suitable. Integration of mechanistic, cyno-electrically-mediated carotid arterial thrombosis (ECAT) concentration-response data with PK/PD platelet aggregation utilizing 12.5, 25, 50 and 100 uM AP suggest that concentrations of BMS-986141 need to exceed certain thresholds to maintain efficacious inhibition of platelets. Thus, dose selection utilizes steady state trough concentrations as an efficacy target. Upon dosing 4 mg of BMS-986141, two Badimon chamber runs are planned. One at Tmax, which maximize the percentage of participants exceeding the ECAT drug concentration that gives 80% of Emax (EC80), and the second 24 hours after dosing which will maximize the percentage of participants exceeding the ECAT concentration for 50% efficacy (EC50). This evaluation will allow for an assessment of thrombus size reduction at each ECAT target to support dose selection optimization under various background therapies including aspirin monotherapy, ticagrelor monotherapy, and dual antiplatelet therapy (aspirin + ticagrelor).

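### Section 10.3.3 specifies no modelled per-arm change from baseline with a CI: neither model is said to be fitted by arm, and the supplemental model has no arm-by-run term

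*Combined protocol and SAP*

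**What the plan says.** The primary objective in Section 4 is "To assess the effect of BMS-986141 alone and as add on to ticagrelor, aspirin, or the ticagrelor + aspirin combination", each compared with pretreatment. Section 5.5 says that the results are meant "to support dose selection optimization under various background therapies".

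Section 10.1 bases the sample size on precision within an arm: a 95% CI half-width on the log scale of 0.146 with 15 participants and 0.188 with 10, using a change SD of 0.263.

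Section 10.3.3 gives two mixed models for log thrombus area:

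- **Main model:** "models separately by shear rates (Low or High) with perfusion run (baseline, 2 hours, and 24 hours) as fixed effects", with participant random.
- **Supplemental model:** also by shear rate, "with treatment arm, perfusion run (baseline, 2 hours, and 24 hours) as fixed effects and participant as a random effect".

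It adds that mean differences from baseline and "the 95% CI of mean differences on the log scale will be estimated from the models", then exponentiated to ratios. By-arm output does appear, in descriptive form: "All thrombosis chamber endpoints will be listed, plotted and summarized by treatment arm, shear rate, and perfusion run". The section also plans plots of geometric mean percent changes in the biomarkers for each arm. Section 10.3 calls this text a summary and defers detail to an SAP due before database lock. No separate SAP is in the supplied text.

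**The concern.** Section 10.3.3 names shear rate as the unit of fitting and does not name arm. An additive arm term moves each arm's level of thrombus area up or down. It cannot let the change from baseline differ between arms. Followed literally, each model therefore returns a single 2 h ratio and a single 24 h ratio per shear rate, averaged over healthy volunteers on BMS-986141 alone and patients on three different background therapies.

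That average is a fair estimate if all four arms share one effect. If they do not, it misstates individual arms, and its interval is about half as wide as the per-arm interval for which the study was sized. The two readings give different primary results, so the choice should not be left until data are in hand.

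**Working it through.** **Inputs.** Change SD on the log scale 0.263 and arm sizes 15, 15, 15 and 10 (Section 10.1); three perfusion runs per participant (Section 5.1).

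**1. The plan's own figures.** Half-width = t(0.975, n−1) × 0.263/√n.

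- n=15: 2.145 × 0.0679 = 0.146
- n=10: 2.262 × 0.0832 = 0.188

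Both match Section 10.1, and only as within-arm intervals. So per-arm estimation is what the study was sized for.

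**2. What each model would deliver.** Assumptions: change SD 0.263 in every arm, complete data, equal variances and equal correlations across runs, one thrombus value per run. The standard error of a change is then 0.263/√n; only n and the degrees of freedom differ.

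| Fit | df | Half-width, n=15 | Half-width, n=10 |
|---|---|---|---|
| As literally written, all 55 participants | 2×54 = 108 | 0.070 (common) | 0.070 (common) |
| Main model by arm | 2×(n−1) = 28 or 18 | 0.139 | 0.175 |
| Arm-by-run term, one residual variance | 2×(55−4) = 102 | 0.135 | 0.165 |

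For example, pooled: 1.982 × 0.263/√55 = 0.070; by arm with n=15: 2.048 × 0.0679 = 0.139.

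At a true ratio of 0.80 (log −0.223) with n=15, the interval is exp(−0.223 ± 0.070) = 0.75 to 0.86 pooled, and exp(−0.223 ± 0.139) = 0.70 to 0.92 by arm.

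**3. Does the arm main effect change anything?** With complete data it does not alter the run contrasts. In one simulated data set with arms of 15, 15, 15 and 10, the run-only model and the arm-plus-run model both gave −0.2866 at 2 h and −0.2505 at 24 h (SE 0.0335). Adding arm-by-run recovered the four separate 2 h changes (−0.123, −0.307, −0.366, −0.384).

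**4. Illustration of misstatement.** The reductions of 15%, 20% and 30% are those tabulated in Section 10.1; assigning them to arms as 15/20/30/30% is an assumption. The common log change is [15×(−0.163) + 15×(−0.223) + 25×(−0.357)]/55 = −0.267, a ratio of 0.77 (95% CI about 0.71 to 0.82). The true arm ratios would be 0.85, 0.80, 0.70 and 0.70.

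**5. Shared variance in the interaction model.** Let the healthy-volunteer SD be k times the patient SD (k assumed). The pooled residual variance, in patient units, is (84 + 18k²)/102, where 84 = 3×28 df comes from the patient arms and 18 df from Arm 4. At k=1.5 this is 1.221, while Arm 4's own variance is 2.25. Its standard error is therefore understated by √(2.25/1.221) = 1.36, and simulated coverage of its 95% CI was about 85%.

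**6. Separate and conditional: high-shear strips.** Section 5.1 states that "The shear rate on the second and third chambers will be high", so a run has two high-shear strips. Suppose, which no section states, that both enter as rows with only a participant random effect. Let f be the share of within-participant variance common to the two strips of a run (assumed). For n=15 the residual df is 90−15−2 = 73, and the standard error is understated by √[(1+f)/(1−17f/73)]: 1.15, 1.30 and 1.46 at f = 0.25, 0.50 and 0.75. Simulated coverage (20,000 arms) was 91%, 87% and 82%. Averaging the strips kept it at about 95%.

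**The case against.** The strongest reply is that a by-arm main fit is plainly meant. Section 4 frames the objective by background, the Section 10.1 half-widths reproduce only within an arm, and step 3 shows that a pooled main model would make the supplemental model redundant. This stands as a reading of intent, but the words are still missing. The supplemental model, as written, cannot yield an arm-specific change under either reading.

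A second reply is that Section 10.3 is a summary and an SAP will follow. That also stands in part: the SAP may settle the point, and this cannot be checked here. Section 10.3 lists participant selection and the handling of missing, unused and spurious data as SAP content. It does not expressly promise model terms.

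Third, the study is sized on precision rather than power, so no error rate turns on the wording. True, but the interval is then the primary result itself.

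A reader might go further and infer that the trial will report only a pooled effect, or no results by arm. The documents do not support that, because by-arm listings, plots and summaries are planned. A reader might also infer that both the by-arm fit and the interaction are required. They are alternatives: once the main model is fitted by arm, a main-effects supplemental model is a legitimate pooled summary if labelled as such.

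On the strips, Section 5.1 refers to standard site procedures and Section 9.8 to a total thrombus area. Handling may be fixed elsewhere, so the documents do not show that the high-shear intervals will be too narrow.

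**Conclusion.** The point holds as a gap in specification that should be closed before database lock. As written, neither primary-endpoint model gives an arm-specific change from baseline, and no modelled per-arm ratio with a 95% CI is specified, although the study was sized on exactly that. It is not evidence that a wrong analysis will be run, since a by-arm main fit is probably intended.

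The difference between the readings is a log-scale half-width of 0.070 for one common effect against about 0.139 (n=15) and 0.175 (n=10) per arm. These figures need the assumptions in step 2, including equal between-run correlations as well as equal variances. The documents do not say which shear rate, or what handling of strips, the SD of 0.263 reflects. The coverage figures in steps 5 and 6 rest on assumed variance ratios and shares. The strip issue is separate and applies only if strips are entered as separate rows.

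**What to change.** In Section 10.3.3 and the SAP:

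1. Choose one of two routes. Either state that the main model is fitted separately by treatment arm and shear rate, or add a treatment arm by perfusion run term and report within-arm contrasts. The by-arm fit is simpler because it does not assume that patients and healthy volunteers share one residual variance.
2. Report the 2 h and 24 h ratios to baseline with 95% CIs for each arm as the primary result.
3. Label any main-effects estimate as a pooled average over arms.
4. As a separate clarification, state the high-shear unit of analysis: average the two strips per run, or include a participant-by-run random effect.

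The cost is a few sentences of wording before lock; data, participants and sample size do not change. The price is wider intervals than the pooled one: 0.139 and 0.175 by arm, or 0.135 and 0.165 with the interaction, against 0.070. Under the stated assumptions these remain in line with the planned 0.146 and 0.188.
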